A urine sample for drug screen and pregnancy test (if applicable), psychiatrist assessment, physical exam, collection of weight and vitals can be completed at either Baseline 1 or Baseline 2.

For Baseline 2 (~1.5 hours), recent depressive symptoms will be assessed via the Inventory of Depressive Symptomatology—Self-Report^{37,40} 30-item version (IDS-SR₃₀), and drinking behavior will be characterized using the Penn Alcohol Craving Scale³¹ (PACS), safety and side effects will be assessed with the Psychobiology of Recovery in Depression III - Somatic Symptom Scale⁴² (PRD-III), the Abnormal Involuntary Movement Scale⁴³ (AIMS), Barnes Akathisia Scale⁴⁴ (BAS) and Simpson-Angus Scale⁴⁵ (SAS), and Go/No-go task.^{46, 47}. The Treatment Impressions Inventory (TII) is a survey about the participants' feelings and impressions towards medical treatment. The TLFB will be repeated to account for drinking behavior since the last visit and CIWA-Ar will account for any withdrawal symptoms. The aripiprazole or placebo capsules will be initiated at 2 mg/day in the morning, increased (if well tolerated) to 5 mg at week 1, 10 mg at week 2 and 15 mg/day (or equivalent placebo) at week 3. Participants taking concomitant medications that are strong inhibitors of the 3A4 or 2D6 isoenzymes will be titrated to a maximum dose of 10 mg/day. Strong CYP3A4 inhibitors are the following: Atazanavir, Boceprevir, Clarithromycin, Cobicistat, Conivaptan, Curcumin, Danazol, Danoprevir, Darunavir, Delavirdine, Diltiazem, Ditiocarb, Econazole, Efavirenz, Elvitegravir, Ergotamine, Idelalisib, Indinavir, Itraconazole, Ketoconazole, Lonafarnib, Loperamide, Lopinavir, Methimazole, Midostaurin, Naloxone, Nefazodone, Nelfinavir, Nilotinib, Posaconazole, Ribociclib, Ritonavir, Saquinavir, Stiripentol, Telaprevir, Telithromycin, Terfenadine, Tipranavir, Troleandomycin, Voriconazole. Strong CYP2D6 inhibitors are the following: Thioridazine, Paroxetine, Cinacalcet, Bupropion, Methotriptane, Fluoxetine, Midostaurin, Propafenone, Glycerol phenylbutyrate, Halofantrine, Cisapride, Dacomitinib, Orphenadrine, Quinidine. For patients taking strong CYP3A4 inducers, the aripiprazole or placebo capsules will be initiated at 4 mg/day in the morning, increased (if well tolerated) to 10 mg at week 1, 20 mg at week 2 and 30 mg/day (or equivalent placebo) at week 3. Participants taking strong CYP3A4 inducers will not be enrolled in the extension phase.

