Strong CYP3A4 inducers are the following: Nevirapine, Rifabutin, Rifampicin, Carbamazepine, Fosphenytoin, Pentobarbital, Phenobarbital, Phenytoin, Primidone, Rifapentine, Enzalutamide, Lumacaftor, St. John's Wort, Mitotane, Apalutamide, and Quinine.

Week 1, 2, 3, 5, 7, 9, 10, 11 (~2 hours each): Subjects will complete the YMRS, HRSD₁₇, CIWA-Ar, TLFB, IDS-SR₃₀, PACS, PRD-III, AIMS, BAS, SAS, and a urine sample will be collected for a drug screen. Subjects will meet with the psychiatrist for weekly assessment and vitals will be collected. In addition, all participants will receive one-hour sessions of manual-driven Medical Management (MM), specifically designed for persons with BPD and substance abuse, provided by an experienced therapist.

Week 4, 8 (~2.5 hours each): Subjects will complete the YMRS, HRSD₁₇, CIWA-Ar, TLFB, IDS-SR₃₀, PACS, PRD-III, AIMS, BAS, SAS, MM, and a urine sample will be collected for a drug screen and pregnancy test. Subjects will meet with the psychiatrist for weekly assessment and vitals will be collected. Blood will be drawn for CBC, CMP, GGT, and CDT.

Week 6 (~2.5 hours): Subjects will complete the YMRS, HRSD₁₇, CIWA-Ar, TLFB, IDS-SR₃₀, PACS, PRD-III, AIMS, BAS, SAS, GNG, MM, and a urine sample will be collected for a drug screen. Subjects will meet with the psychiatrist for weekly assessment and vitals will be collected.

Week 12 (~3.5 hours): Subjects will complete the YMRS, HRSD₁₇, CIWA-Ar, TLFB, IDS-SR₃₀, PACS, PRD-III, AIMS, BAS, SAS, GNG, BIS-11, MM, and a urine sample will be collected for a drug screen and pregnancy test. Subjects will meet with the psychiatrist for weekly assessment and vitals will be collected. Blood will be drawn for CBC, CMP, hs-CRP, GGT, CDT, lipids, and for aripiprazole levels. An exit survey will also be administered to participants evaluating their perception of in-person vs. virtual study visits. In the event of early discontinuation, the survey will be administered at the last available study visit.

At the end of the week 12 treatment phase, participants in both treatment arms who are taking 15 mg/day of aripiprazole (or placebo) and with at least one heavy drinking day will be asked to continue in a 4-week extension phase. Participants taking 3A4 or 2D6 inhibitors will be excluded from this phase. Those in the active treatment group will be increased to 30 mg/day while those in the placebo arm will remain on placebo.

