Clinical information will be obtained via the Structured Clinical Interview for DSM (SCID)³², the Clinical Institute Withdrawal Assessment of Alcohol Use-Revised³⁵ (CIWA-Ar), the Hamilton Rating Scale for Depression³⁴ 17-item version (HRSD₁₇), Inventory of Depressive Symptomatology—Self-Report³⁷⁻⁴⁰ 30-item version (IDS-SR₃₀), Young Mania Rating Scale³³ (YMRS), Penn Alcohol Craving Scale³¹ (PACS), the Psychobiology of Recovery in Depression III - Somatic Symptom Scale⁴² (PRD-III), Abnormal Involuntary Movement Scale⁴³ (AIMS), Barnes Akathisia Scale⁴⁴ (BAS) and Simpson-Angus Scale⁴⁵ (SAS), the Barratt Impulsiveness Scale³⁶ (BIS-11), the Go/No-go task.^{46, 47}, the Timeline Follow Back^{29, 30} (TLFB).

Biological information will be obtained via blood drawn (18mLs) for laboratory analyses including a complete blood count (CBC) and Comprehensive Metabolic Panel (CMP, includes a liver panel with AST, ALT, as well as lipids), high-sensitivity c-reactive protein (hs-CRP), gamma glutamyl transferase (GGT), carbohydrate-deficient transferring (CDT), and aripiprazole levels. In addition, blood will be obtained at baseline (with the participant's consent) for genotyping (an additional 20mLs). A redraw may be requested if the first sample cannot be processed. A physical examination will be performed, weight obtained, and a urine sample collected for a drug screen and pregnancy testing.

9. Recruitment Methods and Consenting Process:

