Participants will be recruited from the community through advertisements, by previous contact with the Psychoneuroendocrinology Research Program (PNE), and by referrals. Recruitment can be challenging in dual-diagnosis studies. By limiting enrollment to the subgroup of people with AUD who also have BPD or Schizoaffective Disorder (bipolar type), the rate of enrollment is generally not as fast as in studies of patients with AUD alone. However, we have had great success in recruiting this patient population. Over the past 16+ years, we have conducted some of the largest trials in BPD and substance use, including trials of quetiapine in patients with BPD and alcohol dependence with 90 and 115 participants. Our success in recruiting participants for our previous and ongoing studies demonstrates that we have the resources and contacts necessary to recruit participants for this project, and that we already have established measures in place to accomplish our recruitment goals. Potential participants who are referred to us or who respond via the various recruitment strategies will be contacted by telephone. Participants who remain interested and eligible for participation based on the telephone prescreen may be asked to come into our clinic for a diagnostic screening visit. Once noted as eligible, the staff member will discuss the procedures they will undergo if they choose to participate in the study. After reading the informed consent, study staff will discuss these issues with the potential participant and will answer any questions he or she may have about the study and participation. If the individual chooses to sign the informed consent document, he or she may begin testing for the study.

10. Potential Risks:

Study Procedure/Intervention

Aripiprazole may cause some, all or none of the side-effects listed below.

	Frequent 30% of subjects	Occasional 15% of subjects	Rare Less than 1% of subjects
Serious	Increased blood sugar	Uncontrolled movements Orthostatic Hypotension	Decreased white blood cell count Seizures
Less Serious	None	Headache Insomnia	None

		Anxiety Nausea Weight gain	
Minor	None	Constipation Vomiting	None

Black Box Warning

WARNING: INCREASED MORTALITY IN ELDERLY PATIENTS WITH DEMENTIA-RELATED PSYCHOSIS and SUICIDAL THOUGHTS AND BEHAVIORS WITH ANTIDEPRESSANT DRUGS

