4) *Assess rates of attrition, safety and tolerability of aripiprazole.* Length of time in the study in weeks will be compared between groups using Cox proportional hazards regression. Scores on the PRD-III, AIMS, BAS and SAS will be compared between-groups as with the Primary Aim above.

5) *Examine genotype as a predictor of response to aripiprazole.* The purpose of this analysis is to identify whether genotype (e.g. 1438A polymorphism in the promoter region of the 5-HT2A receptor, LL compared with the LS/SS of the 5-HTLPR promoter region of the 5-HTT) is a moderator of treatment effect. Treatment effect is determined by treatment group, main effect and treatment group by time interaction effect estimated from the random regression model described for the primary aim. The potential moderator of genotype will be included in the random regression model for the primary outcome along with variable by treatment group interaction and variable by treatment group by time interaction. Significance for either interaction term would indicate that the variable is a moderator.

6) *Explore safety, tolerability and efficacy of an increase in aripiprazole from 15 mg to 30 mg at week 16 for those with at least one drinking day at week 12.* All lab values and other safety measures will be compared between treatment groups at week 16 using t-test or chi-square test, as appropriate. Scores on outcomes measures including alcohol use (e.g. heavy drinking days) and side effect scales (e.g. BAS) will be compared between groups at week 16 using analysis of covariance. Week 12 value of the outcome will be the covariate.

7) *Determine if inflammation decreases with aripiprazole as compared to placebo and whether change in an inflammatory biomarker is associated with change in clinical outcomes.* Analysis described for Exploratory Aim 3 (above) will be used with hs-CRP data to test this aim.

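### Weight gain is a listed risk, but no visit after baseline requires a weight, and no between-arm comparison of weight, glucose or lipids is specified for the 12-week randomised phase

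*Combined protocol and SAP*

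**What the plan says.** **Risks named.** The Section 10 table puts "Increased blood sugar" in the serious row under the frequent (30%) heading. Weight gain stands in the less serious row ("Anxiety Nausea Weight gain"), apparently under the heading "Occasional 15% of subjects". The table is broken in the text available, so that column is inferred from the cell's position. The text below the table adds raised lipids and promises that glucose and lipids will be checked at entry and during the study. It makes no such promise for weight.

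**Schedule.** At baseline, Section 4 says "collection of weight and vitals can be completed at either Baseline 1 or Baseline 2". At weeks 1 to 12, 14 and 16 the physical measures are given as "Subjects will meet with the psychiatrist for weekly assessment and vitals will be collected", without weight. Section 8 says "A physical examination will be performed, weight obtained, and a urine sample collected for a drug screen and pregnancy testing", with no visit attached. The metabolic panel is drawn at baseline and at weeks 4, 8, 12 and 16. The baseline text describes the panel as including lipids, and the week-12 text lists them separately: "Blood will be drawn for CBC, CMP, hs-CRP, GGT, CDT, lipids, and for aripiprazole levels".

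**Analysis.** Under Exploratory Aim 4 (attrition, safety, tolerability), Section 14 compares time in study by Cox regression and then states: "Scores on the PRD-III, AIMS, BAS and SAS will be compared between-groups as with the Primary Aim above". Laboratory values compared between arms over the 12 weeks are CDT, GGT, AST and ALT (Primary Aim, secondary outcomes) and hs-CRP (Exploratory Aim 7). Exploratory Aim 6 compares all laboratory values and other safety measures at week 16, in the extension phase.

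**The concern.** A change in weight needs at least two weights. A site that follows Section 4 to the letter records one. The protocol would then have told participants that weight gain is a risk without collecting what is needed to say whether it happened more often, or by how much, on aripiprazole than on placebo.

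Glucose and lipids are in a different position. They are to be measured, but no analysis of them is named for the phase in which the randomised groups are intact.

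Section 11 says that the drug may have fewer metabolic side effects than most other atypical antipsychotics, and Aim 4 sets out to assess safety and tolerability. A report of good tolerability based on the analyses listed would rest on retention, a somatic symptom scale and three movement scales. It would contain no measured weight change and no prespecified metabolic comparison.

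**Working it through.** This is mainly a check of the schedule against the analysis plan. The plan's one design figure comes first, because it limits what an added comparison could show.

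**1. Sample size (Section 14).** Inputs: standardised effect 0.5, two-sided alpha 0.05, power 80%, t-test. The noncentral t calculation gives 63.77, so 64 per arm and 2 × 64 = 128. Allowing for 3% early loss, 128 / 0.97 = 131.96, so 132. Both stated figures reproduce, and this point does not dispute them.

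**2. Weight, visit by visit (Section 4).**

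| Visit | Vitals named | Weight named |
|---|---|---|
| Baseline 1 or 2 | yes | yes |
| Weeks 1, 2, 3, 5, 7, 9, 10, 11 | yes | no |
| Weeks 4, 8 | yes | no |
| Week 6 | yes | no |
| Week 12 | yes | no |
| Weeks 14, 16 (extension) | yes | no |

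Post-baseline visits: 8 + 2 + 1 + 1 + 2 = 14. Visits among them that name weight: 0. Because the baseline text lists weight and vitals as two items, the word vitals at later visits cannot safely be read to include weight.

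**3. Metabolic measures, analysis by analysis (Section 14).**

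| Analysis | When, and in whom | Weight | Glucose, lipids |
|---|---|---|---|
| Primary Aim models | 12 weeks, all with post-baseline data | no | no (CDT, GGT, AST, ALT) |
| Aim 4 | randomised phase | no | no (time in study, PRD-III, AIMS, BAS, SAS) |
| Aim 7 | baseline to week 12 | no | no (hs-CRP) |
| Aim 6 | week 16, extension only | not scheduled at week 16 | yes, if drawn |

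Planned between-arm comparisons of weight, glucose or lipids over the 12-week phase: 0.

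**4. Does Aim 6 fill the gap?** Extension entry depends on drinking at week 12. Section 4 requires a heavy drinking day, while Section 3 and the Section 14 wording of Aim 6 require a drinking day; either way, selection comes after randomisation. Section 4 also limits entry to those taking 15 mg/day or placebo and leaves out users of 3A4 or 2D6 inhibitors and of strong 3A4 inducers. The active arm's dose has changed by week 16. The result therefore does not estimate the 12-week effect in the randomised sample.

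**5. What an added comparison could show.** For a continuous measure with m per arm, the 95% confidence interval half-width in SD units is t(0.975, 2m − 2) × √(2/m). This simple form ignores any gain from baseline adjustment.

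| m per arm | Half-width (SD) | Detectable difference at 80% power (SD) |
|---|---|---|
| 64 | 0.35 | 0.50 |
| 40 | 0.45 | 0.63 |
| 20 | 0.64 | 0.91 |

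The 64 is the planned evaluable number with equal arms and no later dropout. The 40 and 20 are assumptions that show the effect of missing data.

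**The case against.** **Safety is watched in other ways.** Participants see a psychiatrist and complete the PRD-III at every clinic visit after baseline, a physician investigator evaluates reported adverse events, and the week-18 call asks about side effects. An unblinded DSMB meets after 25, 50, 75 and 100 enrolments and at the end. This stands in part. A reader might infer that the trial could not notice weight gain in anyone, and that goes too far, since a participant may report it. But reports do not replace measurement, Section 11 does not name weight or glucose for DSMB review, and the numerical flag concerns total SAEs.

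**Weight may be taken anyway.** The undated sentence in Section 8 also covers urine tests, which are repeated, so it need not mean baseline only. That is fair, but it requires no weight at any later visit. If sites do weigh participants, stating it costs nothing.

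**The laboratory data exist.** This stands. A reader might infer that the trial cannot assess any metabolic risk. That holds only for measured weight; for glucose and lipids the comparison is unspecified, not unobtainable. Nor is it right that laboratory values are compared only at week 16, given the five markers compared over the 12 weeks.

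**Size.** It is tempting to multiply the 15% and 30% headings by the size of the active arm to predict how many would be affected. The documents do not support that. The headings run 30%, 15% and below 1%, leaving the range between 1% and 15% uncovered, so they read as category labels. Insomnia sits in the 15% column, yet Section 11 cites about 12% at week 1 falling to 5% at week 3.

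**Aim 4 is exploratory.** It is, and this limits the weight of the point without removing it.

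**Conclusion.** The point holds in two parts of different strength. For weight, 0 of 14 post-baseline clinic visits require it, so the plan as written cannot estimate measured weight change by arm. For glucose and lipids, the plan as written does not compare them between arms over the 12-week randomised phase, although the measurements are to be made. Aim 6 does not make up for either.

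This rests on reading vitals as not including weight, as the baseline text does, and on the undated Section 8 sentence not being a follow-up requirement. It also assumes that glucose is read from the metabolic panel; the documents say only that it will be checked. The column in which weight gain sits is inferred, but its listing as a risk is not.

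The primary and secondary efficacy conclusions are untouched. The consequence is confined to what the trial can say about metabolic tolerability, and correcting it is a cheap improvement worth making.

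**What to change.** 1. **Section 4:** name weight at the visits that already draw blood (weeks 4, 8, 12 and 16) and at the last in-person visit of anyone who stops early. Date the mention of weight in Section 8 to match.
2. **Section 14, Aim 4:** add a between-arm comparison of weight, glucose and lipids over the 12-week phase, in all treated participants with data, adjusted for the baseline value. Report estimates with confidence intervals, since precision will be modest. State which draws supply glucose and lipids, as lipids are listed by name only at baseline and week 12.
3. **Aim 6:** keep it, described as a separate comparison in a selected subset.

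Cost: about a minute per visit and a few more safety tables, with no new blood draws. The week-12 exit survey asks about face-to-face and remote visits, so some visits may be remote; weight will be missing for those, and the number missing should be reported by arm.

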At the participant's last visit, the participant will be detitrated according to the following schedule:

- If at **10 mg qAM**: 5 mg qAM for 2 days, then 2 mg qAM for 2 days
- If at **15 mg qAM**: 10 mg qAM for 2 days, then 5 mg qAM for 2 days, then 2 mg qAM for 2 days
- If at **30 mg qAM**: 15 mg qAM for 2 days, then 10 mg qAM for 2 days, then 5 mg qAM for 2 days, then 2 mg qAM for 2 days

If the patient is taking strong CYP3A4 inducers, the participant's last visit, the participant will be debranded according to the following schedule:

- If at **10 mg qAM**: 4 mg qAM for 2 days
- If at **20 mg qAM**: 10 mg qAM for 2 days, then 4 mg qAM for 2 days
- If at **30 mg qAM**: 20 mg qAM for 2 days, then 10 mg qAM for 2 days, then 4 mg qAM for 2 days,

Subjects will be discontinued from the study if any of the following conditions occurs: change in diagnosis to other than bipolar I, II, or NOS disorder and AUD, development of active suicidal or homicidal ideation with plan and intent, worsening in mood symptoms, that in the opinion of the investigators requires discontinuation, pregnancy, development of severe or life-threatening medical condition, involuntary psychiatric hospitalization or incarceration, or significant alcohol withdrawal (e.g. delirium tremens) based on clinical judgment (increases in CIWA-Ar scores will initiate a careful clinical assessment of possible worsening of withdrawal symptoms).

4. Study Procedures:

Baseline: This visit will be split into two portions, Baseline 1 and Baseline 2.

For Baseline 1 (~3 hours), the psychiatric diagnoses will be confirmed by the structured clinical interview for DSM (SCID)³², mania assessed via the Young Mania Rating Scale³³ (YMRS), depression via the Hamilton Rating Scale for Depression³⁴ 17-item version (HRSD₁₇), potential withdrawal symptoms from alcohol via the Clinical Institute Withdrawal Assessment of Alcohol Use-Revised³⁵ (CIWA-Ar), recent alcohol use (and, if present, other substance use) will be assessed using the Timeline Follow Back^{29, 30} (TLFB) method, impulsivity will be assessed with the Barratt Impulsiveness Scale³⁶ (BIS-11), and blood will be drawn for complete blood count (CBC), Comprehensive Metabolic Panel (CMP, includes a liver panel with AST, ALT, as well as lipids), high-sensitivity c-reactive protein (hs-CRP), gamma glutamyl transferase (GGT), and carbohydrate-deficient transferring (CDT). If the subject elects to participate, blood will also be collected for genotyping.

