Participants will be offered an optional genetic component of their study participation and will not be prevented from participating if they choose to not contribute to this genetic component. Additional blood (20mLs) will be drawn if this component is elected. These blood samples will be sent for genotyping to UT Southwestern McDermott Center for Human Growth and Development. Genetics studies implicate the T102C HTR2A polymorphism,^{48, 49} and -1438 A/G polymorphism of the serotonin 2A (5-HT2A) receptor gene,⁵⁰ as well as the rs7916403 in serotonin receptor gene HTR7 on chromosome 10q235,⁵¹ (both receptors with affinity for aripiprazole) in alcohol dependence. Impulsivity in alcohol dependence is also associated with the -1438A polymorphism in the promoter region of the 5-HT2A receptor.⁵² The L/L genotype of the 5-HTTLPR promoter region of the serotonin re-uptake transporter (5-HTT) is associated with early onset of AUD and reduction in alcohol use with ondansetron.⁵³⁻⁵⁵ Alcohol-dependent persons homozygous or heterozygous for the seven (or longer)-repeat allele of the DRD4 VNTR responded to olanzapine with reductions in cue-elicited craving as well as alcohol consumption.⁵⁶ We will also consider adding additional genetic analyses if promising new associations should emerge (e.g. a predictor of aripiprazole response for mood symptoms), based on the available literature at the time of the analysis.

6. Criteria for Inclusion of Subjects:

- Outpatient men and women age 18-70 years old with bipolar I, II or NOS disorder, or Schizoaffective Disorder (Bipolar Type) on the SCID and confirmed by interview with a psychiatrist.
- Current diagnosis of AUD with at least moderate severity (DSM-5 terminology).
- Alcohol use (by TLFB) of an average of 15 drinks per 7 days in the past 28 days prior to intake for men and an average of 8 drinks per 7 day period in the past 28 days prior to intake for women.
- If diagnosis of: Bipolar I, Bipolar NOS with history of mania, or Schizoaffective Disorder (Bipolar Type): Current mood stabilizer therapy (lithium, valproic acid, lamotrigine, gabapentin) with stable dose for \geq 21 days prior to randomization. Patient who meet criteria for these diagnoses, but are not on mood stabilizers at the time of screening will be prescribed Lithium Carbonate (600mg daily) or Valproid Acid (500mg daily) prior to randomization, and are required to be on a stable dose for \geq 21 days before starting Aripiprazole/placebo.

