- Fluent in English or Spanish.
- SBP $>$ 100 and $<$ 165 and DBP $>$ 60 and $<$ 105 with no evidence of orthostatic hypotension

7. Criteria for Exclusion of Subjects:

- Cyclothymic disorder
- Schizophrenia
- Schizoaffective disorder (Depressed type)
- Any psychiatric disorder only due to alcohol use (alcohol-induced mood disorder)
- Any psychiatric disorder only due to substance use (substance-induced mood disorder)
- Any psychiatric disorder only due to a general medical condition
- Baseline HRSD17 or YMRS scores \geq 35 to exclude those with very severe mood symptoms at baseline.
- Evidence of clinically significant alcohol withdrawal symptoms defined as a CIWA-Ar score of \geq 10.
- Use of other substances is allowed if alcohol is the self-identified substance of choice and severity of other substance use disorder is \leq the severity of the Alcohol Use Disorder (DSM-5).
- Current (last 28 days) treatment with an antipsychotic.
- Prior treatment with aripiprazole within the past year, or intolerable side effects to aripiprazole in lifetime.
- Current (last 28 days) treatment with naltrexone, acamprosate, disulfiram or topiramate.
- History of neuroleptic malignant syndrome or tardive dyskinesia.
- Vulnerable populations (e.g. pregnant, nursing, cognitively impaired, incarcerated).
- High risk for suicide defined as $>$ 1 attempt in past 12 months that required medical attention, any attempt in the past 3 months or current suicidal ideation with plan and intent such that outpatient care is precluded.
- Intensive outpatient treatment (defined as \geq 3 visits each week) for substance abuse (AA, NA meetings, or less intensive counseling at baseline will be allowed).

- Severe or life-threatening medical condition (e.g. hepatic cirrhosis) or laboratory or physical examination findings consistent with serious medical illness (e.g. dangerously abnormal electrolytes).
- AST or ALT > 3 times upper limit of normal.
-

8. Sources of Research Material:

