baseline use of psychotropic medications, and change in use of psychotropic medications. Covariates will be included if they significantly improve the fit of the final model. An a priori alpha of 0.05 will be used for all other analyses. The influence of exit aripiprazole blood levels on the primary, secondary and exploratory aims will also be examined.

Secondary Aim: 1) *Determine if aripiprazole as an add-on therapy is associated with a greater reduction in alcohol craving than placebo therapy in outpatients with BPD or Schizoaffective Disorder (bipolar type) and AUD.* PACS scores will be compared between groups with an ITT sample and using a random regression as described above.

Additional Exploratory Analyses:

1) *Determine if aripiprazole as an add-on therapy is associated with a greater reduction in manic and depressive symptoms than placebo therapy in outpatients with BPD or Schizoaffective Disorder (bipolar type) and AUD.* Between-group differences in YMRS, HRSD₁₇ and IDS-SR₃₀ scores will be compared using a random regression as above.

2) *Determine whether changes in alcohol craving and mood occur before or after changes in alcohol use with aripiprazole.* We will explore correlations between baseline to exit changes in mood (e.g. HRSD₁₇) and alcohol use/craving assessments using a Pearson's correlation coefficient in aripiprazole and placebo groups. In addition, a panel model with lagged effects⁵⁹ will be used to analyze 12-week longitudinal data (SAS Proc Panel) in order to explore serial correlations between changes in alcohol use with mood and craving with lagged effect (e.g. one week, two week). Panel model will be constructed for each alcohol use, alcohol craving, depressive and manic symptom, and cognitive outcome, and test if change in alcohol use follows changes in craving, mood or cognition at subsequent visits and vice versa.

3) *Determine if impulsivity decreases with aripiprazole as compared to placebo and examine relationships between change in impulsivity and change in alcohol consumption.* BIS-11 and GNG scores will be compared between groups as with the Primary Aim above. Correlations between BIS-11 scores and GNG scores, and alcohol use measures, as well as lagged effects will be compared as with Exploratory Aim 2 above.

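### YMRS and HRSD17 are scored only at Baseline 1, so for participants who must first start lithium or valproic acid the mood baseline and the severity exclusion appear to pre-date that run-in

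*Combined protocol and SAP*

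**What the plan says.** Section 4 (Study Procedures) says of the baseline: "This visit will be split into two portions, Baseline 1 and Baseline 2". It gives no interval or maximum window between the two.

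- **Baseline 1:** SCID; "mania assessed via the Young Mania Rating Scale"; "depression via the Hamilton Rating Scale for Depression" (17-item); CIWA-Ar; TLFB; "impulsivity will be assessed with the Barratt Impulsiveness Scale"; and blood for CBC, CMP (with AST, ALT and lipids), hs-CRP, GGT and CDT.
- **Baseline 2:** IDS-SR30, PACS, the side-effect scales, Go/No-go and the TII. Of the Baseline 1 measures, two recur: "The TLFB will be repeated to account for drinking behavior since the last visit and CIWA-Ar will account for any withdrawal symptoms". The start of capsules is described next.
- **Either portion:** urine tests, psychiatrist assessment, physical examination, weight and vitals. No rating scale and no blood test is on this list.

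Section 6 (Inclusion) covers bipolar I, bipolar NOS with past mania, and schizoaffective disorder of bipolar type. Participants with these diagnoses who take no mood stabilizer at screening "will be prescribed Lithium Carbonate (600mg daily) or Valproid Acid (500mg daily) prior to randomization", and need at least 21 days on a stable dose before study drug.

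Section 7 (Exclusion) rules out a baseline HRSD17 or YMRS of 35 or more, "to exclude those with very severe mood symptoms at baseline", and AST or ALT above three times the upper limit of normal.

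Section 14 (Biostatistics) compares YMRS, HRSD17 and IDS-SR30 by random regression (Exploratory 1). Exploratory 2 includes "correlations between baseline to exit changes in mood", with HRSD17 as the example, and alcohol use or craving.

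**The concern.** A baseline should describe the participant just before study drug. For those who must first start a mood stabilizer, the only pre-treatment YMRS and HRSD17 scores appear to come from before that new drug. Change from baseline in these scales would then contain any response to lithium or valproic acid as well as what happens on study drug.

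The measures are also not aligned with one another. HRSD17 would be dated before the run-in and IDS-SR30 after it, although both are depression outcomes of Exploratory 1. In Exploratory 2, an HRSD17 change that spans the run-in would be correlated with a PACS change that does not.

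The severity exclusion is meant to describe participants at baseline, but as written it can rest only on the Baseline 1 scores. The same holds for the AST/ALT exclusion and the Baseline 1 blood.

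**Working it through.** The plan states no figure on this point to reproduce. The check is one of order, then dates, then size.

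**1. Order.** The SCID is at Baseline 1 (section 4). The payment text in section 4 has ineligibility found at Baseline 1. Section 9 has consent signed before study testing begins. A prescription required by the study would therefore follow consent and diagnosis, and must precede the first dose by at least 21 days. That places the run-in between Baseline 1 and first dose. No text says so outright, and none provides for repeating the Baseline 1 scales afterwards.

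**2. Dates.** Take the earliest case, a prescription on the day of Baseline 1, and ignore any time needed to reach a stable dose.

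| Later point | Days from first dose | Minimum days from Baseline 1 |
|---|---|---|
| First dose | 0 | 21 |
| Week 1 YMRS, HRSD17 | 7 | 7 + 21 = 28 |
| Week 4 bloods | 28 | 28 + 21 = 49 |
| Week 12 BIS-11, hs-CRP | 84 | 84 + 21 = 105 |

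**3. Size.** The documents give neither the affected share f nor the correlations, so both are assumed: f from 0.10 to 0.40; correlation r = 0.6 between any two readings at unit variance; and, in affected participants only, a correlation of baseline with later readings of 0.4, a fall of Δ = 0.2.

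With t₀ the baseline time, t̄ the mean visit time and Sxx = Σ(t − t̄)², the fitted slope has:

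- variance in unaffected participants: (1 − r)/Sxx
- extra variance in affected participants: 2Δ(t₀ − t̄)²/Sxx²
- relative rise in affected participants: [2Δ/(1 − r)] × (t₀ − t̄)²/Sxx = [0.4/0.4] × (t₀ − t̄)²/Sxx

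The overall rise is f times the last line.

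| Measures | Time points through week 12 | (t₀ − t̄)²/Sxx | Overall, f = 0.10 | Overall, f = 0.40 |
|---|---|---|---|---|
| YMRS, HRSD17 | 13 (weeks 0–12) | 36/182 = 0.198 | +2.0% | +7.9% |
| CDT, GGT, AST, ALT | 4 (weeks 0, 4, 8, 12) | 36/80 = 0.45 | +4.5% | +18% |
| BIS-11, hs-CRP | 2 (weeks 0, 12) | 36/72 = 0.50 | +5% | +20% |

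The two-point row agrees with the change-score formula 2(1 − r): 0.8 at r = 0.6 and 1.2 at r = 0.4, a rise of 50%, times f.

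The model in section 14 also has random slopes. Their variance is added to the slope variance with or without the misdating, so the percentages would be smaller.

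**The case against.** The strongest objection is that the order is inferred. Section 4 treats the baseline as a single visit in two parts, section 6 ties the prescription to screening, and section 9 mentions a diagnostic screening visit before consent. If the run-in were finished before Baseline 1, nothing would be misdated. This stands as a limit on certainty. It does not remove the point, because a study-required prescription before consent and before the SCID is the less natural reading, and the plan nowhere states it.

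Four stronger readings are tempting, and the documents do not support them.

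- **Bias in the treatment effect.** A reader might infer that the lithium or valproic acid response distorts the comparison. Both arms pass through the run-in before study drug, and randomization is stratified by lithium versus anticonvulsant. Any shift is expected equally in both arms.
- **Damage to the main drinking and craving results.** TLFB is repeated at Baseline 2 and PACS is taken there. No TLFB defect is shown, so nothing calls for redefining the drinking baseline or the drinks-per-drinking-day stratum.
- **A 5–20% loss of precision in the mood scales.** That range belongs to two-point measures. YMRS and HRSD17 have twelve readings after baseline. The lagged panel model of Exploratory 2 uses the 12-week series, so the mismatch falls mainly on the simple correlation. In Exploratory 3, BIS-11 and Go/No-go are each compared between arms, so having baselines on different dates distorts neither comparison.
- **No oversight during the run-in.** A psychiatrist assessment may fall at Baseline 2, serious illness on laboratory or physical findings is excluded, section 11 relies on physician judgment, and the mood scales recur at week 1 and the CMP at week 4. What is missing is a written re-check of the scores, not oversight.

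**Conclusion.** The point holds on the most natural reading of the visit order. In participants who must start a mood stabilizer, the YMRS and HRSD17 baseline and the exclusion at 35 or more are dated at least 21 days before study drug and before a new mood drug, while IDS-SR30 and PACS are dated after it. Change from baseline in the exploratory mood analyses is misdated, and the HRSD17–craving correlation pairs changes over different periods.

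The effect is added noise and blurred interpretation, not bias between arms. Under the assumed share and correlations it is modest for the weekly mood scales and larger in proportion only where there are few readings. The true size is unknown because the documents do not say how many participants are affected. The conclusion does not depend on the assumed figures; it rests on the visit lists and on the inferred order.

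**What to change.** 1. Add YMRS and HRSD17 to Baseline 2, before the first capsule, for all participants.
2. State in section 14 that the Baseline 2 scores are the baseline in every mood analysis, including the Exploratory 2 correlations.
3. State where the run-in falls relative to Baseline 1 and Baseline 2. Reconcile sections 4, 6 and 7 on when the existing HRSD17/YMRS and AST/ALT exclusions are judged relative to it.

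The cost is a slightly longer Baseline 2 visit. Staff already give both scales at every later clinic visit.

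I would not add a second blood draw. It is an extra procedure, and the gain is limited to less noise in secondary and exploratory measures. BIS-11 and the bloods would keep their Baseline 1 date, and the plan should say so.
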